### 5.3.8 Study duration, treatment exposure and compliance

The overall study duration for each subject will be approximately 62 weeks (6-week screening period, 52-week treatment period and 4-week follow-up period).

Study duration (days) will be calculated as:

- End of study date - Date of informed consent +1.

Due to the Covid-19 pandemic, some visits were postponed, and study duration can exceed 62 weeks (6-week screening period, 12-month treatment period and 4-week follow-up period) for the concerned subjects. Study duration will be summarized for the Safety set overall and by treatment group. The number (%) of subjects with a study duration exceeding 62 weeks will also be tabulated.

Treatment exposure will be based on:

CONFIDENTIEL / Ne pas diffuser sans autorisation de DBV

CONFIDENTIAL / Do not distribute without DBV authorization

	Statistical Analysis Plan	
	EPITOPE (V712-304) – Statistical Analysis Plan	
	Référence du Document /Document Reference : CCI	Page : 33 / 74

CCI

- The exposure duration (in days, regardless of treatment interruption), calculated over the whole study period as:
  - Date of last patch application – Date of first patch application) +1,
- The total dose of peanut protein (in mg) received via the patch during the study, calculated over the whole study period as:
  - Exposure duration (in days) \* Actual treatment dosage

Exposure duration and total peanut protein dose will be summarized for the Safety set overall and by treatment group (except total peanut protein dose that will only be described for the active arm).

Number and percentage of subjects per category of exposure duration (in days) will be presented using the following categories:

- 0 to 6 months (Day 1 to Day 180),
- 6 to 12 months (Day 181 to Day 365),
- 12 to 18 months (Day 366 to Day 545),
- > 18 months (> Day 546)

The compliance (%) determined over the whole study period as:

$$100 \times \left( \frac{\text{Number of patches dispensed} - \text{Number of patches returned}}{\text{Exposure duration in days}} \right)$$

Global compliance will be summarized for the Safety set overall and by treatment group.

Treatment compliance will be summarized using frequency tables (<80%, 80% to 100%, >100) and by means of descriptive statistics (n, mean, SD, median, Q1, minimum, Q3, and maximum) with compliance > 100% set to 100%.

If a subject did not bring back unused patches, the amount of patches that have been applied cannot be accurately assessed. During the Data Review Meeting, before database lock, each subject having unreturned kit will be evaluated and a decision will be taken whether the subject compliance should be considered as missing.

The study medication must be applied on the skin for 24 hours every day ( $\pm 4$  hours), except during the initiation of treatment, where the duration of application of the study medication will be progressively increased as follows:

- During the first week (from Day 1 through Day 7), the patches will be applied for 2 hours ( $\pm 30$  minutes) every day;
- During the second week (from Day 8 through Day 14), the patches will be applied for 4 hours ( $\pm 30$  minutes) every day;
- During the third week (from Day 15 through Day 21), the patches will be applied for 8 hours ( $\pm 1$  hour) every day;
- During the fourth week (from Day 21 through Day 28), the patches will be applied for 12 hours ( $\pm 2$  hours) every day;

CONFIDENTIEL / Ne pas diffuser sans autorisation de DBV

CONFIDENTIAL / Do not distribute without DBV authorization

	Statistical Analysis Plan	
	EPITOPE (V712-304) – Statistical Analysis Plan	
	Référence du Document /Document Reference : CCI	Page : 34 / 74

CCI

- From the fifth week onwards (Day 29), the patches will be applied for the entire 24 hours ( $\pm 4$  hours) every day.

The time to first 24 hours ( $\pm 4$  hours) patch application will be summarized by means of descriptive statistics (n, mean, SD, median, Q1, minimum, Q3, and maximum) and described using a Kaplan Meier curve.

The daily application duration (in hours) will be summarized descriptively using the subject e-diary data for the following periods:

- Overall,
- D1 to D7,
- D8 to D14,
- D15 to D21,
- D22 to D28,
- D29 to D90,
- D91 to D185,
- D186 to D275,
- D276 to D365,
- > D365,
- D29 to D365,
- > D29

If more than one patch is applied the same day, the daily duration considered is the cumulative application duration of these patches (if the end date/time of first patch is not documented, the application date/time of the next patch will be used for imputation).

The percentage of days with no patch application, per subject e-diary reported data, will also be tabulated, overall and for each of the above periods.

A patch will be considered as “applied” if the date and time of application is documented in the e-diary.

The start date/time and/or end date/time of patch application used to calculate the duration of patch application are extracted from the e-diary.

If the duration calculation leads to an aberrant value (ie. a negative value or a value  $> 50h$ ), then the duration will be considered as missing.

Average duration of application will be calculated:

- On patches with available duration only
- On all patches using 0-imputation (section 5.2.4) when duration is not available (e.g. missing date or time of removal)

All data including documentation of treatment interruptions will be listed.

CONFIDENTIEL / Ne pas diffuser sans autorisation de DBV

CONFIDENTIAL / Do not distribute without DBV authorization

	Statistical Analysis Plan	
	EPITOPE (V712-304) – Statistical Analysis Plan	
	Référence du Document /Document Reference : CCI	Page : 35 / 74

CCI

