**Part B**

The sample size for the efficacy part of the study is calculated based on the following assumptions:

- A 2:1 ratio in favor of the DBV712 dose *versus* placebo;
- A 40% response rate for DBV712 (optimal active dose) and a 10% response rate for placebo using missing=failure imputation method (based on a maximum drop-out rate of 15%). This will give a 30% absolute difference for the primary endpoint between active and placebo at 12 months of treatment;
- A lower bound of the 95% confidence interval (CI) of the difference between the selected active treatment and placebo response rates  $\geq 15\%$ ;
- Newcombe method is used for the computation of the CI.

Hence, the minimum number of subjects needed to ensure a power of at least 90% is 350 (approximately 233 subjects in total in the selected active DBV712 group [250 µg] and 117 subjects in the placebo group).

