### 3.4 Justification of the Study Design

This study is designed to assess the efficacy and safety of DBV712 at either 100 µg or 250 µg in children aged 1 through 3 years compared to placebo.

Randomized, double-blind and placebo controlled design was chosen to prevent bias in treatment allocation and in the assessment of both safety and efficacy.

The use of a placebo group in this study is justified to obtain reliable scientific evidence for the evaluation of this new medicinal product.

The first part of the study (Part A) is designed to assess the safety and tolerability of the two doses of DBV712 patches, 100 µg or 250 µg, in this pediatric population. At the time of initiation of EPITOPE study, these two DBV712 doses had been previously tested in several clinical studies in very young children: PEP01.09 study with children from 6 years of age, ARACHILD study with children from 5 years of age, Phase IIb VIPES study with children from 6 years of age and CoFAR6 study with subjects from 4 years of age (34).

No dose-dependent difference regarding the patches local tolerance was identified on the peanut protein doses range 50 to 250 µg. High incidences of local skin reactions from any grade of severity (1 to 3) are reported: 90% to 98%, with very low incidence leading to treatment discontinuation (1.2% in VIPES Study). No difference in local tolerance was identified between the age groups.

Since no children less than 4 years old was treated by DBV712, two doses were selected for this study: the 250 µg dose selected as the therapeutic dose for children aged from 6 to 12 years old, and the lower dose of 100 µg, to deal with possible poor tolerance to the 250 µg dose in younger children.

The safety and tolerability evaluation and dose selection was to be performed after 3 months of active treatment. In the previous Viaskin® clinical studies, a vast majority of the local tolerance issues has emerged within the first month of treatment. The analysis after 3 months of treatment should allow a reliable assessment of the local tolerability and to confirm the tolerance of the two doses (Upon review of the 3-month safety data, both doses were considered as safe by the DSMB, and the highest [250-µg] dose was selected for Part B).

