### 4.3 Patient Withdrawal and Replacement

#### 4.3.1 Subjects Stopping Rules

Subjects must be withdrawn from the study treatment under the following circumstances:

- Severe anaphylaxis (stage 3 anaphylaxis, see [APPENDIX 4](#)) related to Viaskin® patch application (either peanut or placebo patch);
- More than 2 intramuscular epinephrine injections for an AE related to Viaskin® patch application (either peanut or placebo patch), and not occurring during the DBPCFC nor related to an accidental food allergen consumption.

Subjects may be required to be withdrawn from the study treatment or study after discussion with the Investigator and/or Sponsor for the following reasons:

- AE(s);
- Severe “maculo-papular rash” or severe generalized atopic “dermatitis” outside of patch application area, which failed to be controlled by adequate corrective treatments (including topical corticosteroids) and in spite of several study treatment interruptions;
- At the discretion of the Investigator, if she/he decides that it is in the subject’s best interest to be withdrawn from the study;
- The subject is unwilling to continue in the study (consent withdrawal);
- Lack of compliance with protocol requirements and procedures;
- The subject fails to return to the clinic for scheduled visits and does not respond to telephone or written attempts at contact (lost to follow-up);

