Some subjects may have a higher skin reactivity at the initiation of the treatment, leading to uncomfortable sensations or intense pruritus. These local reactions usually decrease over time as far as the treatment continues. However, some subjects may have difficulties in bearing these uncomfortable sensations or intense pruritus. In these subjects, it is recommended to remove the patch as soon as the subject starts complaining, to clean and to wash the skin area and if necessary use topical corticosteroids. The next patch will be applied the following day on the next skin zone as scheduled. The duration of patch application could usually be increased with time, up to the final targeted 24 hours of patch application; therefore, the treatment initiation period could be longer than the 4 weeks proposed above, until tolerance to Viaskin® patch treatment is achieved per the Investigator's assessment.

If possible, the parents or guardians should take advantage of the child bath/shower time to change the patch. The previous Viaskin® patch should be removed just before the bath/shower, and the new Viaskin® patch should be applied a few minutes after the bath/shower and after drying the skin carefully. Application of the Viaskin® patch at a similar time for each daily application (morning or evening) is recommended. If the child does not bathe or shower daily or at the same time daily, it is recommended that the zone where the patch will be applied be cleaned with a moist disposable napkin or tissue and dried prior to application.

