## 5.3 Subject characteristics

### 5.3.1 Subject disposition

A clear accounting of the disposition of all subjects who enter the study will be provided, from screening to study completion. Subject disposition will be summarized for all subjects, overall and by treatment group. Percentages will be based on the number of subjects in the Full Analysis Set (FAS). The following descriptions will be performed on all enrolled subjects:

- Number of enrolled subjects, number of screen failures, reasons for non-randomization,
- Analysis sets: number and percentage of subjects in each population used for the analyses. The populations are defined in Section 4.
- Number and percentage of subjects who completed the study treatment, subjects who discontinued the study treatment and reasons why subjects discontinued the study treatment,
- Number and percentages of subjects who discontinued the study treatment:
  - Before Month 12 (exposure < 358 days)

CONFIDENTIEL / Ne pas diffuser sans autorisation de DBV

CONFIDENTIAL / Do not distribute without DBV authorization

	Statistical Analysis Plan	
	EPITOPÉ (V712-304) – Statistical Analysis Plan	
	Référence du Document /Document Reference : CCI	Page : 27 / 74

CCI

- At Month 12 or after (exposure  $\geq$  358 days)
- Number and percentages of subjects who performed the Month 12 Food Challenge:
  - As per Month 12 time-window
  - Out of Month 12 time-window (visit delayed due to covid-19 pandemic)
- Number and percentage of subjects randomized by region, country and site,
- An enrolment summary will be presented overall, by region, country and site, showing the number of subjects enrolled, randomized and completing the study, the first date of consent, the last study visit date, the study duration (in days, calculated as the end of study date for randomized subjects – first date of consent for the first screened subject +1).

Study disposition and termination details will be listed for each subject. Listings will also be created to show the study analysis set classifications and randomization assignments.

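### The Kaplan-Meier curve for time to first 24-hour patch wear has no censoring or competing-event rule; if children who stop first are censored, it overstates the proportion reaching full wear

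*SAP*

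**What the plan says.** The step-up schedule in SAP 5.3.8 ends at Day 29: "From the fifth week onwards (Day 29), the patches will be applied for the entire 24 hours". Protocol 5.2 allows a slower course for children who find the patch hard to bear, so that "the treatment initiation period could be longer than the 4 weeks proposed above", and sets no upper limit on that extension.

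For the time to first 24 h (±4 h) application, SAP 5.3.8 plans two outputs. It will be "summarized by means of descriptive statistics (n, mean, SD, median, Q1, minimum, Q3, and maximum", and it will be "described using a Kaplan Meier curve". SAP 5.1 makes presentation by treatment group the default.

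The SAP does not say how this outcome treats three kinds of children:
- those who stop patches before 24 h wear;
- those still on treatment without 24 h wear when observation ends;
- those whose patch durations are set to missing as aberrant.

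No competing event is named. Stopping can certainly occur: Protocol 4.3.1 has a list beginning "Subjects must be withdrawn from the study treatment under the following circumstances", followed by discretionary reasons that include adverse events and uncontrolled severe rash.

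**The concern.** Permanent discontinuation before the first 24 h patch rules the event out, so it is a competing event. Kaplan-Meier with such children censored treats them as if they would go on to 24 h wear at the same rate as those who continue. One minus Kaplan-Meier then describes a hypothetical setting in which nobody stops. It no longer gives the proportion of treated children who reach full wear.

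The stopping is also plausibly informative. Protocol 5.2 describes children with intense pruritus who need longer to build up wear time, and the withdrawal reasons in Protocol 4.3.1 include adverse events. Poor tolerance can therefore both delay the event and cause the stop. If that is more common on active treatment than on placebo, the bias would differ by arm and flatten the contrast that the curve is meant to show.

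What is at stake is the reading of tolerability during the step-up in children aged 1 to 3. The primary and secondary efficacy results are not affected.

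**Working it through.** The documents give no figure for time to 24 h wear, so there is none to reproduce. The check asks how far one minus Kaplan-Meier (1−KM) can lie above the cumulative incidence when children who stop first are censored.

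**Inputs from the documents.**
- Earliest scheduled 24 h wear: Day 29 (SAP 5.3.8).
- Planning drop-out: the Part B sample-size text in the protocol synopsis sets its response rates "based on a maximum drop-out rate of 15" per cent. That is a maximum over 12 months, for any reason.
- Discontinuation for local skin reactions: 1.2% in an earlier study of older children (Protocol 3.4).

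**Assumptions, not in the documents.**
- First 24 h wear comes from Day 29 onwards, with a median of 10 extra days.
- 5%, 10% or 15% of children stop. They stop evenly over 12 months, all within 90 days, or all before Day 29.
- 0%, 5% or 10% would never reach 24 h wear even if they stayed.

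**Bound.** Kaplan-Meier passes the weight of each censored child to those still at risk. At most, all of that weight becomes events. Hence (1−KM) − cumulative incidence ≤ proportion who stop before the event. At 1.2% stopping, the excess is at most 1.2 points.

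**Simulation to Day 365, 50,000 children per scenario, all who stay reaching 24 h wear.** Here 1−KM is 100% throughout. Cells show the cumulative incidence, with the excess of 1−KM in percentage points.

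| Timing of stopping | 5% stop | 10% stop | 15% stop |
|---|---|---|---|
| Evenly over the year | 99.5% (0.5) | 98.8% (1.2) | 98.3% (1.7) |
| All within 90 days | 97.8% (2.2) | 95.3% (4.7) | 93.0% (7.0) |
| All before Day 29 | 95.0% (5.0) | 90.2% (9.8) | 84.9% (15.1) |

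The 15.1 against a bound of 15 is simulation error.

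**Hand check.** When everyone who stays reaches 24 h, the excess equals the probability of stopping first, roughly the stopping proportion × mean time to event ÷ stopping window. A median of 10 extra days gives a mean of 10 ÷ ln 2 = 14.4, so the mean time is about 29 + 14.4 ≈ 43 days.
- Evenly over the year at 15%: 0.15 × 43/365 ≈ 1.8 points, against 1.7 simulated.
- Within 90 days at 15%: 0.15 × 43/90 ≈ 7.2 points, against 7.0 simulated.

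**If some children never reach 24 h although they stay.** With 10% such children and 15% stopping, 1−KM levels off near 90%. The cumulative incidence is 88.3%, 83.8% and 76.1% for the three timings. The curve no longer approaches 100%, but the overstatement remains.

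**Sensitivity.** With 15% stopping evenly over the year, a median delay of 3, 30 or 90 days gives an excess of 1.2, 3.0 or 5.1 points. If the children who stop are exactly those who have not reached 24 h, and they stop in the 60 days after Day 29, the excess is 5.0, 9.9 and 14.9 points for 5%, 10% and 15% stopping. That is again essentially the bound.

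**The case against.** The strongest reply is that the SAP nowhere says that children who stop are censored. A reader might infer it, because it is the usual default, but the text gives no rule. If those children were kept at risk to the end of follow-up, the curve would show the crude proportion without this bias. That stands, and it is why the point is conditional. The documented gap is the missing rule, and without one two programmers could draw different curves.

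A reader might also infer that the curve must climb to about 100% however many children stop. The documents do not support this. The initiation period has no upper limit, so children may stay on treatment without reaching 24 h wear, and they hold the curve down.

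Nor is the curve the only information on tolerating the step-up:
- SAP 5.1 defines n as subjects with non-missing data. If only children who reached 24 h have a time, n over the Safety set gives the crude proportion, although the SAP does not say so for this outcome.
- SAP 5.3.8 tabulates daily wear time and days without a patch by period.
- SAP 5.3.1 tabulates discontinuations with reasons, but splits their timing only at 358 days.
- SAP 5.5.1.3 tabulates adverse events leading to permanent or temporary discontinuation.

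These outputs limit the harm. None of them states how many treated children ever reached 24 h wear.

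Finally, the 15% is a planning maximum for the Month 12 analysis, not a rate of stopping before 24 h wear, and the 1.2% figure suggests that the effect could be small. Both points stand. The 1.2% comes from older children, and Protocol 3.4 chose a slower step-up partly because local tolerance is harder to assess in young children, so it does not settle the matter for this age group.

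**Conclusion.** The point holds in conditional form. SAP 5.3.8 names Kaplan-Meier for an outcome that permanent discontinuation rules out, and states no censoring or competing-event rule. If children who stop first are censored, 1−KM overstates the proportion of treated children who reach full wear, by no more than the proportion who stop first.

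The excess is about 0.5 to 1.7 points for 5 to 15% stopping evenly over the year, and about 2 to 7 points if all stop within 90 days. It reaches 5 to 15 points only if all the stopping precedes 24 h wear, of which stopping entirely before Day 29 is the clear case. Stops at the 1.2% rate of the earlier study could add at most about 1.2 points. These sizes rest on assumed timing of stopping and an assumed median delay of 10 days after Day 29. The bound does not.

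This is a minor matter. The display is descriptive, and no test, success criterion or efficacy conclusion depends on it.

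**What to change.** In SAP 5.3.8, replace the Kaplan-Meier curve with a cumulative incidence (Aalen-Johansen) curve by arm. Take permanent treatment discontinuation before the first 24 h patch as the competing event. Censor only children still on treatment without the event at the end of observation. State how patches with missing or aberrant durations count towards the event. Beside the curve, report n/N (%) of the Safety set who ever reached 24 h wear, by arm.

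The cost is a sentence or two in the SAP and a different plotting call. No new data are needed and no other analysis changes. The one downside is that the reported proportion reaching 24 h wear becomes slightly lower.

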## 5.4 Efficacy Analyses

Intercurrent events defined for efficacy are summarized in the following table.

**Table 3 - Intercurrent Event Types**

Label	Intercurrent Event Type	Comment (for main estimand)
Intercurrent event 1 (Early treatment Discontinuation before 12 Months*)	Treatment exposure < M12 and missing peanut DBPCFC	Subjects will be included in the FAS. Subjects will be considered as a non-responder.
Intercurrent event 2 (subject/caregiver refusing the Month 12 peanut DBPCFC)	Treatment exposure $\geq$ M12, subject had not started the peanut DBPCFC and refusing to ingest the peanut formula	Subjects will be included in the FAS. An imputation will be used for missing data.
Intercurrent event 3 (peanut DBPCFC initiated but not finished)	Child starting the DBPCFC and stopped without symptoms leading to ending the peanut DBPCFC (stopping rules) (e.g. refusing to ingest the peanut formula left due to fear, aversion)	Subjects will be included in the FAS. An imputation will be used for missing data.
Intercurrent event 4 (peanut DBPCFC completed at Month 12* falls outside the recommended time-window)	Delayed peanut DBPCFC completed at Month 12 (e.g. due to temporarily closed centers or postponed visits (COVID-19))	Subjects will be included in the FAS. Actual values will be used regardless of whether an intercurrent event has occurred.
Intercurrent event 5 (discontinuation at or after Month 12 * with Month 12 peanut DBPCFC missing)	Treatment exposure $\geq$ M12 but missing peanut DBPCFC (e.g. due to temporarily closed centers or postponed visits (COVID-19))	Subjects will be included in the FAS. An imputation will be used for missing data.

\*Month 12 time windows are comprised between 358 – 407 days (section 5.2.7).

